## **Participants**

### Sample size estimation

A total of 154 participants will be enrolled at the three participating clinics. The following assumptions were used to derive this sample size:

Proportion of Placebo+MM/MC participants achieving >95% adherence = 20%

Proportion of Vivitrol+MM/MC participants achieving >95% adherence = 40%

Power=72%

Alpha level=0.05

Participants at the Nathan Smith Clinic will be 50 HIV-infected men and women who report heavy drinking, alcohol abuse or dependence. Referrals will come from within the Nathan Smith Clinic site, via local HIV care sites, website advertisements, local papers, community postings, community physicians, other patients, local mental health centers, local hospitals, and substance abuse treatment facilities.

***Inclusion criteria:*** Each subject must:

1. Be HIV-infected.
2. Currently be prescribed HAART medication.
3. Report less than 95% adherence to their HAART medication.
4. Report heavy drinking 4 or more times in the past 4 weeks, or meet current criteria for alcohol abuse or dependence. Heavy drinking is defined as 4 or more drinks for women and 5 or more drinks for men on one occasion.
5. Be at least 18 years old.
6. Be able to understand English and provide informed consent.

***Exclusion criteria:*** No subject may:

1. Be psychotic or severely psychiatrically disabled.
2. Be currently enrolled in formal treatment for alcohol (excluding self-help, e.g. Alcoholics Anonymous)
3. Have medical conditions that would preclude completing or be of harm during the course of the study.
4. Have laboratory or clinical evidence of significant liver dysfunction (alanine aminotransferase (ALT) or aspartate aminotransferase (AST) greater than 5 times the upper limit of the normal range) or cirrhosis with a Child-Pugh classification greater than A or B.
5. Have a known contraindication to NTX therapy (e.g. requiring opioid medication for pain).
6. Be pregnant, nursing or unable to use an effective method of birth control (women).
7. Patients with a positive urine opioid screen result
8. Known hypersensitivity to naltrexone, PLG (polylactide-co-glycolide, carboxymethylcellulose, or any other components of the diluent

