**Phosphatidyl ethanol (PEth)**, a phospholipid formed only in the presence of alcohol, has shown 95-100% sensitivity and 100% specificity to detect heavy drinking over a period of 2-3 weeks in several studies of dependent patients and abstainers in Europe. The detection of PEth appears to be dose-dependent. The threshold for PEth is around 1000 grams over 2-3 weeks with a mean daily intake of 50 grams (4.2 standard drinks). The identification of serum PEth will be performed by liquid chromatography-tandem mass spectrometry (LC-MS-MS) as previously described.

**Rates of viral mutations**, according to International AIDS Society guidelines [132], will be determined by collecting plasma and conducting standard HIV drug resistance testing. We will also collect historical genotypic information through chart review. Our team has extensive experience in DNA sequencing techniques and has used these methods in HIV transmission risk studies [34, 133, 134]. For patients with a detectable viral load (>400 HIV RNA copies/mL) we will conduct standard HIV drug resistance testing [34, 133, 134] at baseline and follow up. Standard DNA sequencing will be performed using a consensus population sequencing of the HIV-1 *pol* gene [135]. In addition, a sample from each monthly blood draw will be archived. Ultimately these samples will be processed in a batched fashion and a second aliquot of HIV RNA from the patient sample will be screened for high and low abundance resistant variants (to ~1% levels) by ultra-deep sequencing techniques [33, 38, 136].

**CD4 lymphocyte counts and HIV RNA levels** will be checked at baseline and monthly.

**Potential alcohol/HAART interactions** resulting in hepatotoxicity will be evaluated with monthly liver function tests including AST, ALT and gamma-glutamyl transpeptidase (GGT). We will also collect monthly platelet counts to calculate an AST to platelet ratio index (APRI) and FIB-4. APRI and FIB-4 represent commonly utilized fibrosis indices which provide non-invasive assessments using readily available clinical markers. The AST-platelet ratio index

(APRI) index 
$$\left( \frac{AST * ULN * 100}{platelets} \right)$$
 (calculated as  $[AST \times ULN \times 100] / [\text{platelet count (10}^9/\text{L})]$ )

and FIB-4 score 
$$\left( \frac{age * AST}{ALT * \sqrt{platelets}} \right)$$
 (calculated as  $[age \times AST] / [ALT \times \sqrt{platelets}]$ )

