scores, represent validated surrogate fibrosis indices used to distinguish no or minimal liver fibrosis from advanced fibrosis and cirrhosis. Based on validation studies in a spectrum of cohorts with chronic HCV and HIV infection, scores of  $FIB-4 > 3.25$  were used to designate advanced fibrosis or cirrhosis. Scores of  $FIB-4 < 1.45$  were used to designate the absence of significant fibrosis. Monthly blood work will also include creatinine and hemoglobin levels to incorporate into the VACs Index, a scoring system that assesses both HIV-related and - unrelated morbidity/mortality.

**Sexual risk behaviors** will be measured using a modified assessment incorporating specific questions from the High Risk Behavior Survey (HRBS) [137], a validated instrument that measures sexual risk (non-condom use, multiple partners) behaviors that have been associated in previous studies with HIV serostatus and seroconversion.

**Side effects/adverse experiences** will be collected at each visit using the Systematic Assessment for Treatment Emergent Effects (SAFTEE) [102], a validated measure of side effects in clinical trials.

**The alcohol and drug use disorders** section of the Structured Clinical Interview for DSM-IV-TR Axis I Disorders (SCID-I/P) [138] will assess for past or present alcohol use disorders [139] at baseline.

**Lifetime and current DSM-IV-TR Axis I and II psychiatric disorders** will be assessed using the Structured Clinical Interview for DSM-IV (SCID) [138].

**Blood Alcohol Concentration** (breathalyzer) will be obtained at baseline and at each visit. We will use this data to monitor patients and identify those in whom self-report would be suspect (e.g. BAC  $> 0.4$ ).

**The Addiction Severity Index 5th Edition Lite (ASI-Lite)** will be used to assess the severity of alcohol and any drug dependence and associated psychosocial impairment. This instrument is a modified version of the ASI [140].

**The Brief Symptom Inventory (BSI)** is a multidimensional symptom inventory designed to reflect psychological symptom patterns of psychiatric and medical patients.

**The Short Inventory of Problems (SIP)** is an assessment that measures physical, social, intrapersonal, impulsive, and interpersonal consequences of alcohol and drug consumption.

**The Brief Pain Inventory** is an assessment to measure pain symptoms.

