**Specific Aim 3a:**

To compare differences between the two treatment conditions in the impact on viral mutations, we will use descriptive statistics to report the prevalence of current HIV drug resistance mutation patterns at baseline and at 24-weeks, 9 and 12 months. HIV resistance mutations, as defined by the International AIDS Society guidelines [138], will be evaluated. We will evaluate the association between heavy drinking and HIV viral mutations first in a dichotomous way. We will evaluate the bivariate association of heavy drinking and viral mutations and conduct a chi-square evaluation that contrasts the development of HIV viral mutations (positive vs. negative) with heavy drinking (yes vs. no). Subsequently we will conduct exploratory analyses using multinomial logistic regression to adjust for the potential effects of prior resistance mutations, antiretroviral medication class, duration of HIV disease, and duration of HAART. We will explore the effect of HAART adherence on the relationship between heavy drinking and the development of HIV drug resistance using sequential modeling to test for a potential mediating effect of HAART adherence. Finally, we will conduct an exploratory analysis to determine if the presence and quantity of minor variants affects virologic and HIV outcomes.

To compare differences between the treatment conditions, monthly CD4 lymphocyte counts and HIV RNA will be evaluated using the Mixed Models repeated-measures analysis controlling for baseline differences. To compare differences between the treatment conditions on their impact on liver function tests and Fib-4, we will use the Mixed Models repeated-measures analysis controlling for baseline differences.

We also plan to explore the effect of the treatment conditions on sexual risk behaviors (as measured by the HRBS on a monthly basis). A Mixed Models repeated-measures analysis will be used to evaluate treatment group, time, and interaction effects. We will also collect data on baseline hepatitis status, depressive symptoms at baseline and at the completion of the study, and any side effects reported by patients during the course of the study.

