Audiotaped sessions: Participants will be made aware during the informed consent process that sessions with the study physician or nurse will be audiotaped and that the nature of these sessions will involve participants speaking about information regarding their health status, alcohol use, HIV status, medical history, and participation in the study. However, participant names will never be recorded on the tapes and the tapes will be coded by participant number rather than name in order to protect participant confidentiality. Participants will be given the option to decline to be taped during the study.

**2. Minimizing Risks:** Describe the manner in which the above-mentioned risks will be minimized.

Naltrexone (VIVITROL): Prospective participants with medical conditions that would contraindicate the use of VIVITROL will be screened out. We will exclude individuals with evidence of significant hepatocellular injury (AST, ALT > 5 times the upper limit of normal or a diagnosis of cirrhosis and Child-Pugh class greater than A or B). The dose of VIVITROL used is low and so the risk of hepatotoxicity is low. However, we will monitor liver enzyme tests prior to, during, and at end of treatment and a subject whose AST or ALT rises to > 5 times the upper limit of normal will have laboratory tests repeated in one week. If liver enzymes are persistently elevated or if the individual is symptomatic, study medication will be discontinued and the subject will be referred for GI evaluation.

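### APRI is printed with AST multiplied by the laboratory's upper limit of normal, not divided by it, so its absolute values cannot be read as a fibrosis index

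*Combined protocol and SAP*

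**What the plan says.** Under potential alcohol/HAART interactions in Section V.3 (Baseline and in-treatment assessments), the protocol plans two non-invasive fibrosis scores from monthly blood work: "We will also collect monthly platelet counts to calculate an AST to platelet ratio index (APRI) and FIB-4". The APRI expression follows in the same paragraph, once as a displayed fraction and once in line. Both have AST × ULN × 100 in the numerator and the platelet count (10^9/L) in the denominator. No other section gives a different APRI formula.

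Of the two scores together the protocol says that they "represent validated surrogate fibrosis indices used to distinguish no or minimal liver fibrosis from advanced fibrosis and cirrhosis". Cut-offs follow for FIB-4 only.

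Elsewhere the ULN is used as a yardstick for the enzyme. The liver exclusion criterion (Section V.3, repeated in Section VII.3) applies to ALT or AST "greater than 5 times the upper limit of the normal range". The safety rule in Section IX.2 (Minimizing Risks) concerns "a subject whose AST or ALT rises to > 5 times the upper limit of normal".

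On setting: "A total of 154 participants will be enrolled at the three participating clinics". On analysis, the paragraph under Specific Aim 3a reads, for the comparison of treatment conditions: "impact on liver function tests and Fib-4, we will use the Mixed Models repeated-measures analysis controlling for baseline differences". APRI is not named there.

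**The concern.** A ULN term in an enzyme score puts the enzyme on a common scale, so that a result counts for less where the laboratory's normal range extends higher. Multiplying does the opposite: for the same AST and platelets, the laboratory with the higher limit returns the higher score. The units show the same thing. AST and its limit share units, which cancel under division and are squared under multiplication.

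The expression is a derivation rule, not background text. A programmer who follows it will produce, at every visit, scores of an entirely different order from AST expressed as a multiple of its limit. The level could then not be described as mild or advanced fibrosis. If more than one laboratory limit is in use, part of the spread between clinics would reflect the laboratory and not the liver.

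**Working it through.** **Inputs.** AST = 53 is the median at first date in the table of HIV-infected patients on naltrexone (Section IX.1). The documents give neither the AST limit nor platelet values. I assume ULN from 30 to 50 and platelets of 200 × 10^9/L, with 150 to 250 as a range. The plan gives no APRI value or cut-off, so there is no figure of its own to reproduce.

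**Step 1, the two forms.**

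- Printed: P = AST × ULN × 100 / platelets
- Divided: D = (AST / ULN) × 100 / platelets
- Hence P = D × ULN²

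**Step 2, size and direction**, with AST 53 and platelets 200:

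| Assumed ULN | Printed P | Divided D | P / D = ULN² |
|---|---|---|---|
| 30 | 795 | 0.88 | 900 |
| 35 | 928 | 0.76 | 1225 |
| 40 | 1060 | 0.66 | 1600 |
| 45 | 1193 | 0.59 | 2025 |
| 50 | 1325 | 0.53 | 2500 |

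For example, 53 × 40 × 100 / 200 = 1060, and (53 / 40) × 100 / 200 = 0.66. P rises with the limit while D falls. Over platelets of 150 to 250, P runs from 636 to 1767 and D from 0.42 to 1.18, so the two ranges do not come near each other.

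**Step 3, if laboratory limits differ.** For one patient's AST and platelets, moving from ULN 35 to ULN 40 multiplies P by 40/35 = 1.143 and D by 35/40 = 0.875, a 1.31-fold discrepancy. From ULN 30 to 40 the factors are 1.333 and 0.75, a 1.78-fold discrepancy. Two patients with the same AST multiple and the same platelets, at laboratories with limits of 35 and 50, have identical D but differ in P by (50/35)² = 2.04-fold.

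**Step 4, if one limit applies throughout.** On the log scale, log P = log D + 2 log ULN. With a common ULN the second term is a constant. Ranks, relative changes, and log-scale or standardized treatment contrasts are then the same for P and D, and only the absolute level is wrong.

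**Step 5, where the score is used.** The planned mixed models under Specific Aim 3a cover liver function tests and FIB-4. The fibrosis cut-offs are for FIB-4. Eligibility and safety monitoring use AST and ALT directly. None of these takes APRI as an input.

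**The case against.** Four points can be made on the other side.

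- **The divided form is not written in the documents.** They define APRI only in the multiplied form, and the eligibility and monitoring rules do not say how APRI is built. This is fair as far as it goes. The case for an error rests on the protocol's own reading of AST as a multiple of ULN, on the direction in which the printed score moves, and on the units. Those are enough to show that the expression defeats its stated purpose. The sponsor should still confirm the replacement against its source for the index.

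- **It may be a conversion fault.** A division sign can be lost when an equation is read from PDF. The displayed and in-line versions agree, which makes this unlikely but not impossible.

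- **Pooling across clinics.** A reader might infer that APRI from the three clinics cannot be pooled. The documents do not support this. They state neither the clinics' AST limits nor whether one laboratory is used, and with a common limit pooling does no harm beyond a constant factor.

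- **Bias between arms.** A reader might also infer a biased treatment comparison. Randomization is stratified by clinic, so a clinic-level factor should be roughly balanced between arms. Within a patient whose ULN stays the same, it cancels from relative change. What is left, if limits differ, is mainly extra between-clinic variation on the raw scale.

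The last two points stand and limit the consequence. None of the four makes the printed expression right.

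**Conclusion.** The APRI expression is wrong as written. It moves in the wrong direction with the laboratory limit and is too large by ULN squared: 900 to 2,500-fold for assumed limits of 30 to 50, and 1600-fold at ULN 40. The factor does not depend on AST or platelets. The absolute values cannot be read as a fibrosis index.

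A spurious laboratory effect in pooled raw values is conditional on limits that differ between clinics. The documents leave that open, so the 1.31-, 1.78- and 2.04-fold figures are illustrations and not estimates for this trial.

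The point is minor. The Assessments overview lists alcohol-HAART hepatotoxicity as a secondary outcome, but liver function tests fall under exploratory Aim 3. APRI itself has no cut-off and no named analysis. It would be wrong to infer that the adherence or heavy-drinking results, the planned FIB-4 model, eligibility or safety monitoring are affected by this formula.

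**What to change.** Check the source page first. If it agrees with the text, change both printings to (AST / ULN) × 100 / platelets (10^9/L), and state that ULN is the limit of the laboratory that ran the sample. Record that limit with each AST result. It would help to add one sentence saying whether APRI will be analyzed or only described.

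The cost is one formula, corrected in two places in the protocol and once in the derivation program. AST and platelet counts are collected in any case, so any scores already derived can be recalculated once the applicable limits are known. No visit, sample or sample-size change is needed.

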$$\left( \frac{\text{age} * \text{AST}}{\text{ALT} * \sqrt{\text{platelets}}} \right)$$

(calculated as  $[\text{age} \times \text{AST}] / [\text{ALT} \times \sqrt{\text{platelets}}]$ ), a validated surrogate

serum fibrosis index marker used to distinguish no or minimal liver fibrosis (F0-F1) from advanced fibrosis (F3) and cirrhosis (F4). Based on pivotal validation studies in patients with chronic HCV and HCV-HIV co-infected patients [41, 42], scores of  $\text{FIB-4} > 3.25$  were used to designate advanced fibrosis or cirrhosis (F3-F4). Scores of  $\text{FIB-4} < 1.45$  were used to designate the absence of significant fibrosis (F0-F1). We plan to use FIB-4 in the proposed study as a non-invasive marker of liver fibrosis.

Therefore, based on evidence that even low levels of alcohol can act synergistically with HIV, HCV and HAART to cause hepatotoxicity, strategies that can decrease the adverse impact

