**Medical concerns of NTX treatment in HIV-infected individuals**

***Increased prevalence of hepatitis C (HCV)***

Because of its potential for hepatotoxicity, NTX should be used with caution in individuals with impaired hepatic function. We plan to use low, but effective doses of NTX, and to assess hepatic safety using a standard self report form [102] and serial serum transaminases in the proposed study. Approximately 30% of HIV-infected individuals in the U.S. are co-infected with HCV [103]. HIV has a significant effect on the progression of HCV to severe liver disease [104-106]. After 15 years of infection with HCV, those co-infected with HIV have a 25% risk of cirrhosis, while those with HCV alone have only a 6.5% risk [105]. Co-infection may increase the risk but not the severity of hepatotoxicity from HAART medication, and therefore HAART should not be avoided in these individuals, but transaminases need careful monitoring [103, 107, 108]. VIVITROL can also have hepatotoxic effects, though at higher dosages than will be used in the proposed study. A recent large study of extended release VIVITROL found that mean liver enzymes did not change significantly over the course of treatment and there was no effect of medication on the proportion of patients in the different groups who had liver enzyme elevations higher than several times the upper limit of normal [61]. In addition, it has been found to be safe for use in patients with mild to moderate liver impairment [109] with evidence of a 15% greater reduction in liver enzyme levels in the VIVITROL group as compared with the placebo group [110]. VIVITROL is approved for use in patients who meet criteria for Child-Pugh classification A and B indicating tolerance in patients with impaired hepatic function. While these data are reassuring, monitoring of liver function, to assess for hepatotoxicity, will be important, especially in HIV/HCV co-infected patients.

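### FIB-4 as printed does not fit its own cut-offs for most adults and ignores any proportional change in AST and ALT together; the APRI formula needs clarifying

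*Combined protocol and SAP*

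**What the plan says.** FIB-4 is defined in two places: the Background subsection on liver injury, and Baseline and in-treatment assessments (paragraph on potential alcohol/HAART interactions). Each place gives a displayed fraction and an in-line version, and all four agree: age × AST over ALT × √platelets. The denominators are typeset as "ALT} * \sqrt{\text{platelets" in the Background and within "age * AST}{ALT * \sqrt{platelets" in the assessments section. No other form of the index appears anywhere.

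Both sections give the same cut-offs. Scores above 3.25 indicate advanced fibrosis or cirrhosis, and scores below 1.45 "were used to designate the absence of significant fibrosis".

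The index is meant to be used. The Background says "We plan to use FIB-4 in the proposed study as a non-invasive marker of liver fibrosis", and the statistical text under Specific Aim 3a compares the arms on "liver function tests and Fib-4, we will use the Mixed Models repeated-measures analysis controlling for baseline differences".

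APRI is printed in the same assessments paragraph as AST × ULN × 100 divided by platelets. A platelet unit of 10⁹/L is given there for APRI; none is given for FIB-4.

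**The concern.** A formula and its cut-offs should belong together: ordinary patients should be able to fall on either side of them. Here most adults could not score below the lower cut-off, and many with unremarkable inputs would exceed the upper one. That suggests the square root is on the wrong variable.

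This matters because the score feeds a planned treatment comparison. The printed form is not a constant multiple of the form with the root moved, since it weights ALT and platelets differently, so the error does not cancel between arms. If the program follows the text, an effect of naltrexone that lowers AST and ALT in proportion would appear as no FIB-4 difference. Adjusting for baseline cannot restore information that the score does not carry.

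**Working it through.** **Inputs from the protocol.** The printed formula; cut-offs 1.45 and 3.25; the enzyme effect cited in the hepatitis C subsection of the Background, "evidence of a 15% greater reduction in liver enzyme levels in the VIVITROL group as compared with the placebo group"; and first and last median enzymes in HIV-infected patients on naltrexone, from the laboratory table under Risks (AST 53 then 66; ALT 36 then 48).

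**Assumptions.** The protocol gives no age or platelet distribution. I use platelets of 150–400 ×10⁹/L and show ranges of age and AST/ALT. The protocol contains no worked FIB-4 value to reproduce.

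**Formulas compared.**
- Printed: P = age × AST / (ALT × √platelets)
- Root moved to ALT: E = age × AST / (platelets × √ALT). The protocol does not print this form; it serves here as a comparator.

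**1. Parallel enzyme change.** Multiply AST and ALT by c. P changes by c/c = 1, so not at all. E changes by c/√c = √c. At age 50, platelets 250 and AST = ALT:

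| AST = ALT | P | E |
|---|---|---|
| 25 | 3.16 | 1.00 |
| 50 | 3.16 | 1.41 |
| 75 | 3.16 | 1.73 |
| 100 | 3.16 | 2.00 |

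For a 15% fall, assumed equal in both enzymes, P changes by 0% and E by √0.85 − 1 = −7.8%.

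**2. The score can move against both enzymes.** Between the protocol's medians AST rises 25% (66/53) and ALT 33% (48/36). P changes by (66/48)/(53/36) − 1 = −6.6%; E changes by (66/√48)/(53/√36) − 1 = +7.8%. The AST and ALT medians come from different numbers of patients (52 and 63), so this shows direction only.

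**3. Lower cut-off.** P < 1.45 requires age < 1.45 × √platelets / (AST/ALT):

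| AST/ALT | platelets 150 | 250 | 400 |
|---|---|---|---|
| 0.6 | 29.6 | 38.2 | 48.3 |
| 0.8 | 22.2 | 28.7 | 36.2 |
| 1.0 | 17.8 | 22.9 | 29.0 |
| 1.2 | 14.8 | 19.1 | 24.2 |

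Some adults do qualify: at age 40, ratio 0.6 and platelets 300, P = 40 × 0.6/√300 = 1.39.

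**4. Upper cut-off.** At the first medians (AST 53, ALT 36) and age 50, P runs from 6.01 (platelets 150) to 3.68 (platelets 400). Every value is in the advanced-fibrosis band. E runs from 2.94 to 1.10.

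**5. Illustrative grid.** Ages 30–65 by 5, AST/ALT 0.6–1.5 by 0.1 and platelets 150–400 by 50 give 8 × 10 × 6 = 480 equally weighted combinations. This is not a population estimate. P does not depend on the enzyme level; E does.

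| Form | below 1.45 | above 3.25 |
|---|---|---|
| P | 5.8% | 39.6% |
| E, ALT 25 | 82.1% | 0% |
| E, ALT 40 | 68.8% | 1.7% |
| E, ALT 60 | 54.2% | 5.2% |
| E, ALT 100 | 35.2% | 12.7% |

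**6. Units.** With platelets per microlitre (250,000) and AST = ALT, P > 3.25 needs age > 3.25 × √250,000 = 1,625. Neither unit reconciles the printed form with the cut-offs.

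**7. Platelet weight.** A 20% fall in platelets raises P by 1/√0.8 − 1 = 11.8% and E by 1/0.8 − 1 = 25.0%.

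**8. APRI.** With assumed AST 60 and platelets 200, the literal form gives 60 × 35 × 100/200 = 1,050 at ULN 35 and 60 × 50 × 100/200 = 1,500 at ULN 50. Dividing AST by ULN gives 0.86 and 0.60. Read literally, a higher laboratory limit raises the score instead of lowering it.

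**The case against.** The strongest reply has four parts.

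- **FIB-4 is a fibrosis marker, not an enzyme measure.** Nothing in the protocol says it must respond when AST and ALT move together, and the enzymes are modelled separately. This is fair as far as it goes: insensitivity to parallel change is not by itself a contradiction. The contradiction is between formula and cut-offs; the insensitivity shows what that slip would cost in the planned comparison.
- **The mismatch depends on assumed inputs, and no categorical FIB-4 analysis is planned.** Both statements are true. Young adults, or those with a low AST/ALT ratio, can score below 1.45, and on the grid more than half of the combinations fall between the cut-offs. The mismatch is therefore one of degree. It remains large over ordinary adult ranges, and the continuous analysis is affected whether or not the cut-offs are used.
- **The 15% effect is one-sided.** The same Background subsection also reports a large trial of the extended-release product with no significant change in mean enzymes, and the 15% does not say which enzymes it covers. This stands: 0% against −7.8% illustrates the formula's behaviour and is not a forecast.
- **It may be only a transcription slip, with the correct form in the program.** That is possible. The protocol, however, repeats the same form in two sections and gives no other definition, so a check is needed.

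On APRI, the printed product may be shorthand for AST in multiples of ULN. No APRI cut-off is given and the Aim 3a text does not name it. With a single ULN the literal form is a constant multiple and changes no test. It is a clarification only.

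**Conclusion.** The concern holds. The printed FIB-4 depends on AST and ALT only through their ratio, which is certain from the algebra. Its poor fit to 1.45 and 3.25 rests on assumed but ordinary ages and platelet counts; it holds for most adults, not all. If programmed as written, the Aim 3a comparison would analyse a different quantity from the fibrosis index intended, one that can stay flat or even fall while both enzymes rise.

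The consequences are contained. Liver outcomes belong to exploratory Aim 3, although the assessments overview also lists hepatotoxicity as a secondary outcome. AST, ALT and GGT are measured and liver function tests are analysed separately. The primary adherence outcome, the sample size and the liver-enzyme safety rule do not involve FIB-4. It should be fixed, but it does not threaten the trial's main conclusions. The protocol alone shows that formula and cut-offs disagree; it does not establish which formula was intended, and that must come from the cited sources.

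**What to change.** 1. Check the FIB-4 formula against the two validation studies cited in the Background (references 41 and 42). If they confirm it, replace the printed form in the Background and in Baseline and in-treatment assessments with (age × AST) / (platelets × √ALT).
2. State the platelet unit for FIB-4 beside the formula.
3. Compare the analysis program with the confirmed formula, and recompute any values already derived from the printed one.
4. After a similar source check, write APRI as (AST/ULN) × 100 / platelets (10⁹/L) and say that each laboratory's own ULN applies.

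The cost is corrected text in two sections and a short check of the code. Age, AST, ALT and platelets are already collected, so both indices can be recomputed at any time without new data.
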